10.6.7 Dose Expansion

Part B

The 2 dose expansion levels will be chosen based on peripheral target engagement and non-overlapping PK in order to evaluate intra-tumoural PD activity and help determine the RP2D. One dose expansion level will be the MTD/HPDD and one dose expansion level will be lower than the MTD/HPDD. Each dose level will enrol approximately 20 participants with NSCLC or MSS-CRC (enrolling approximately 10 participants in each tumour type). Expansions may open either in parallel or sequentially at Sponsor's discretion. Expansions may start before the MTD/HPDD has been determined.

Part C

The two efficacy expansions will be determined based on emerging data from Part A and/or Part B and may include two indications at a single dose level or one indication at two dose levels. If the RP2D cannot be adequately determined from Part B and additional data (eg, efficacy) is required to guide RP2D determination, then two dose levels in one indication will be investigated. If the RP2D is determined at the end of Part B, RP2D will be evaluated in two indications. Each efficacy expansion will enrol up to approximately 40 participants which may include up to 10 participants from the relevant Part B expansion. An interim analysis will take place after 20 participants (further details in Section 10.9.5).

10.6.7.1 Treatment Allocation in Dose Expansion Phase

Participants will not be randomised in this study; however, IxRS will be used in all parts of the study to ensure participants receive their allocated medication.

10.6.8 Definition of DLT

Dose limiting toxicity includes event(s) which happen during the 21 days of Cycle 1 of Part A and represent ≥ Grade 3 toxicity, as defined below, which is not clearly attributable to the disease under investigation, other concomitant medications, disease-related processes under investigation, or another non-drug-related aetiology, with modifications or exceptions noted below.

The DLT evaluation period is from the first exposure of AZD8853 until the end of Cycle 1, which is 21 days. All DLTs must be documented as AEs, graded according to

NCI CTCAE v5.0 and need to be followed until improvement to CTCAE Grade < 1. A minimum of at least 3 DLT-evaluable participants are required for the SRC to hold a dose-escalation vote.

An AE not listed below, or an AE meeting the DLT criteria below but occurring outside of the DLT period may be defined as a DLT-like event after consultation with the Sponsor and Investigators based on the emerging safety profile.

The following toxicities constitute a DLT:

- Any death not clearly due to the underlying disease or extraneous causes.
- Grade 4 adverse events of immune nature (imAE).
- Any ≥ Grade 3 non-infectious pneumonitis regardless of duration; diagnosis should include clinical evaluation, monitoring of oxygenation using pulse oximetry (resting and exertion), laboratory workup and high-resolution CT scan.
- Any \geq Grade 3 non-infectious colitis irrespective of duration after confirmation by colonoscopy and histopathology.
- Any Grade 3 imAE, including rash, pruritus, or diarrhoea (NOTE: this excludes colitis or pneumonitis, as these AEs are already defined above), that does not downgrade to Grade ≤ 2 within 7 days after onset of the event despite maximal supportive care including systemic corticosteroids.
- Liver transaminase elevation:
 - i. Criteria for all participants except participants with elevated transaminases (ALT/AST) at baseline/screening due to liver metastasis:
 - Isolated liver transaminase elevation $> 5 \times \text{but} \le 8 \times \text{ULN}$ that does not downgrade to AST/ALT $\le 3 \times \text{ULN}$ within 14 days after onset with optimal medical management.
 - Isolated liver transaminase elevation > 8 × ULN regardless of duration or reversibility.
 - Any increase in AST or ALT > $3 \times \text{ULN}$ and concurrent increase in TBL $\geq 2 \times \text{ULN}$, regardless of duration or reversibility, where no other reason, other than the study intervention, can be found to explain the combination of increases.
 - ii. Criteria for participants with elevated transaminases (ALT/AST) at baseline/screening due to liver metastasis (inclusion criterion 8):
 - Isolated liver transaminase elevation $> 2 \times \text{but} \le 5 \times \text{baseline}$ that does not downgrade to $< 2 \times \text{baseline}$ or less within 14 days after onset with optimal medical management.

- Isolated liver transaminase elevation > 5 × baseline regardless of duration or reversibility.
- Any increase in AST or ALT > $3 \times$ baseline and concurrent increase in TBL $\geq 2 \times$ ULN regardless of duration or reversibility, where no other reason, other than the study intervention, can be found to explain the combination of increases.
- Grade 3 nausea, vomiting, or diarrhoea that does not resolve to Grade ≤ 1 within 3 days of initiation of maximal supportive care.
- Neutropenia:
 - i. ≥ Grade 3 febrile neutropenia regardless of duration ruling out the cause of fever due to non-infections events.
 - ii. ≥ Grade 3 neutropenia, without associated fever or systemic infection, which does not improve by at least one grade within 5 days of onset.
- Anaemia:
 - i. Grade 4 anaemia regardless of duration.
 - ii. Grade 3 anaemia that requires more than one transfusion of > 2 units of red blood cell.
- Thrombocytopenia:
 - i. \geq Grade 4 thrombocytopenia lasting > 7 days.
 - ii. ≥ Grade 3 thrombocytopenia, regardless of duration, associated with haemorrhage.
- Thrombocytopenia in presence of anticoagulation therapy:
 - i. Thrombocytopenia below Grade 3 lasting for 7 days, without additional risk factors.
- Any ≥ Grade 3 neurotoxicity (to include but not limited to limbic encephalitis, autonomic neuropathy, including peripheral neuromotor syndromes such as myasthenia gravis and Guillain-Barré) regardless of duration.
- Any \geq Grade 3 cardiotoxicity (to include but not limited to arrhythmias, myocarditis with cardiomyopathy, ventricular dysfunction) regardless of duration.
- Any ≥ Grade 3 ocular toxicity (including but not limited to iritis, uveitis, significant vision changes) regardless of duration.
- Any other pre-existing toxicity that has worsened as compared to baseline that is clinically significant and unacceptable, does not respond to supportive care, results in a disruption of dosing schedule of more than 21 days or is judged to be a DLT by the SRC.

The DLT definition excludes the following conditions:

- Grade ≥ 3 fatigue lasting ≤ 7 days.
- Concurrent vitiligo or alopecia of any grade.
- Grade 3 or Grade 4 lymphopenia, unless associated with infection.
- Grade 3 or higher amylase or lipase that is not associated with symptoms or clinical manifestations of pancreatitis, irrespective of duration.
- Grade 3 or higher electrolyte abnormality that lasts up to 72 hours, is not clinically complicated, and resolves spontaneously or responds to conventional medical interventions.

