9.6 Safety Review Committee

A study-specific SRC will be responsible for making dose-escalation or dose de-escalation decisions and recommendations regarding further conduct of the study, during all parts of the study. The SRC will provide ongoing safety surveillance of the study, with regularly scheduled reviews of safety and other relevant data to monitor the ongoing safety profile of the study intervention.

The SRC may also meet to review data at other timepoints (eg, in response to AEs assessed as medically relevant by the Study Physician). The SRC will review the totality of the AE, SAE, and laboratory safety data from a minimum of 3 participants who have completed the 21-day DLT period, and all relevant available data, including PK, prior to adjudicating on dose-escalation/de-escalation decisions based on the dose-escalation rules. For each dose cohort, every effort will be made to have all available PK data to the SRC at the time of the dose escalation decision. All decisions by the SRC will be documented and shared with all participating sites in writing. The SRC will be composed of Sponsor representatives and Investigators. The composition and procedures of the SRC will be fully described in the SRC charter.

- **SUBSTUDY 1 10**
- 10.1 **Substudy 1 Summary**
- 10.1.1 Schema

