E 3 Identification of Potential Hy's Law Cases

In order to identify cases of PHL it is important to perform a comprehensive review of laboratory data for any participant who meets any of the following identification criteria in isolation or in combination:

- ALT \geq 3 × ULN
- AST \geq 3 × ULN
- TBL \geq 2 × ULN

Local Laboratories Being Used:

The Investigator will without delay review each new laboratory report and if the identification criteria are met will:

- Determine whether the participant meets PHL criteria (see Section E 2 for definition) by reviewing laboratory reports from all previous visits
- Promptly enter the laboratory data into the laboratory eCRF

E 4 Follow-up

E 4.1 Potential Hy's Law Criteria not Met

If the participant does not meet PHL criteria the Investigator will:

- Inform the AstraZeneca representative that the participant has not met PHL criteria.
- Perform follow-up on subsequent laboratory results according to the guidance provided in the CSP.

E 4.2 Potential Hy's Law Criteria Met

If the participant does meet PHL criteria the Investigator will:

- Determine whether PHL criteria were met at any study visit prior to starting study treatment (see Section E 6)
- Notify the AstraZeneca representative who will then inform the central Study Team

- Within one day of PHL criteria being met, the Investigator will report the case as an SAE of PHL; serious criteria 'Important medical event' and causality assessment 'yes/related' according to CSP process for SAE reporting.
- For participants that met PHL criteria prior to starting IMP, the Investigator is not required to submit a PHL SAE unless there is a significant change[#] in the participant's condition
- The Study Physician contacts the Investigator, to provide guidance, discuss and agree an approach for the study participants' follow-up (including any further laboratory testing) and the continuous review of data
- Subsequent to this contact the Investigator will:
 - Monitor the participant until liver biochemistry parameters and appropriate clinical symptoms and signs return to normal or baseline levels, or as long as medically indicated. Completes follow-up SAE Form as required.
 - Investigate the aetiology of the event and perform diagnostic investigations as discussed with the Study Physician.
 - Complete the three Liver eCRF Modules as information becomes available.

E 5 Review and Assessment of Potential Hy's Law Cases

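### In the DLT rules for transaminases raised at baseline by liver metastasis, 'isolated' is undefined and the combined bilirubin criterion starts above the 14-day criterion, so some combined rises of >2× to ≤3× baseline meet no liver criterion

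*Protocol*

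**What the plan says.** Protocol Section 10.6.8 splits the liver DLT criteria into two lists. List i is for everyone except participants whose transaminases were already raised by liver metastasis. List ii is for those participants, headed "Criteria for participants with elevated transaminases (ALT/AST) at baseline/screening due to liver metastasis (inclusion criterion 8". Each list has three bullets:

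| Bullet | List i | List ii |
|---|---|---|
| Isolated, 14-day | >5× to ≤8× ULN, not down to ≤3× ULN within 14 days | >2× to ≤5× baseline, not down to <2× baseline within 14 days |
| Isolated, immediate | >8× ULN | >5× baseline |
| Combined with TBL ≥2× ULN, no other explanation, any duration | >3× ULN | >3× baseline |

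The immediate bullet of list ii reads "Isolated liver transaminase elevation > 5 × baseline regardless of duration or reversibility". Neither the protocol nor the SAP says what isolated means.

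Other routes exist. The last DLT bullet in Section 10.6.8 begins "Any other pre-existing toxicity that has worsened as compared to baseline that is clinically significant and unacceptable, does not respond to supportive care" and ends "results in a disruption of dosing schedule of more than 21 days or is judged to be a DLT by the SRC". An unlisted event "may be defined as a DLT-like event after consultation with the Sponsor and Investigators based on the emerging safety profile". Section 9.6 adds: "The SRC will review the totality of the AE, SAE, and laboratory safety data from a minimum of 3 participants". Appendix E, on potential Hy's Law (PHL), states: "Within one day of PHL criteria being met, the Investigator will report the case as an SAE of PHL". SAP Section 4.2.1.8.1 takes as reported DLTs those that the SRC has approved and recorded.

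**The concern.** A transaminase rise with raised bilirubin is the more worrying liver signal, so a DLT rule should catch it at least as readily as the same rise alone. In list ii the combined bullet starts at 3 times baseline and the 14-day bullet at 2 times. Whether anything falls between them depends on the undefined word. On the stricter reading, adding raised bilirubin to a persistent rise takes it out of the liver criteria. Two investigators could also classify the same persistent case differently.

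DLT counts drive the mTPI-2 decisions and the MTD estimate in cohorts of 3 to 9, so a single classification can matter. The participants concerned are also those whose liver tests are hardest to interpret.

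**Working it through.** The plan states no figure to reproduce. The check applies the bullets to cases.

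**Inputs.** The thresholds are those tabulated above (Section 10.6.8). Table 6 in Section 5.1 sets entry ALT/AST at ≤5× ULN with liver metastasis, and entry total bilirubin (TBL) at ≤1.5× ULN without Gilbert's syndrome. Appendix E 2 sets PHL at ALT/AST ≥3× ULN with TBL ≥2× ULN.

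**Step 1: order of the thresholds.**
- Combined against 14-day bullet: list i 3/5 = 0.6; list ii 3/2 = 1.5.
- Combined against immediate bullet: list i 3/8 = 0.375; list ii 3/5 = 0.6.

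The order in list ii is reversed against the 14-day bullet only.

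**Step 2: a drug-explained rise to 2.5× baseline under list ii.**

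| TBL | Settled within 14 days | Isolated = bilirubin not raised | Isolated = no bilirubin condition |
|---|---|---|---|
| Normal | No | 14-day bullet met | 14-day bullet met |
| Normal | Yes | None met | None met |
| 2.5× ULN | No | **None met** | 14-day bullet met |
| 2.5× ULN | Yes | **None met** | **None met** |

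The result is the same at 3.0× baseline. At 3.5× baseline with TBL 2.5× ULN the combined bullet is met on either reading. List i shows no such gap: at 3.5×, 5.5× and 8.5× ULN with TBL 2.5× ULN its combined bullet is always met.

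**Step 3: the band in ULN terms.** For a baseline of b × ULN (1 < b ≤ 5), the band runs from above 2b to 3b × ULN, with TBL ≥2× ULN.

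| b | Band (× ULN) |
|---|---|
| 1.2 | >2.4 to 3.6 |
| 1.5 | >3 to 4.5 |
| 2 | >4 to 6 |
| 3 | >6 to 9 |
| 4 | >8 to 12 |
| 5 | >10 to 15 |

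Since 2b ≥ 3 when b ≥ 1.5, from that baseline upward the whole band lies in the PHL range. Without Gilbert's syndrome, reaching TBL 2× ULN from an entry value of at most 1.5× ULN is a rise of at least 2/1.5 = 1.33-fold.

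**Step 4: example at b = 4.** ALT of 11× ULN is 11/4 = 2.75× baseline.
- Unresolved at 14 days with normal bilirubin, it is a DLT. With TBL 2.5× ULN it meets no liver bullet on the stricter reading.
- If it falls to 7× ULN (7/4 = 1.75× baseline) within 14 days, the case with raised bilirubin meets no liver bullet on either reading.

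**Step 5: lowering the combined bullet.** At >2× baseline with no ULN floor, b = 1.2 gives >2.4× ULN. This is below the 3× ULN of list i and of PHL, and the same holds for every b < 1.5. Requiring >3× ULN as well makes the threshold the larger of 2b and 3: 3× ULN up to b = 1.5, 4× at b = 2, 10× at b = 5.

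**The case against.** The strongest reply is that list ii is coherent on a sensible reading. Isolated may mean only that the transaminase value is judged on its own. The 14-day bullet then catches every persistent rise in the band. What remains is rises that settle, which would not be DLTs with normal bilirubin either. The bullet that truly matches the combined one is the immediate one, since both apply at any duration, and there the order holds (3 below 5). This stands as a limit on the concern. It does not remove it, because the protocol does not say which reading applies and the contrast with the combined bullet points to the stricter one.

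A second reply is that DLTs are adjudicated. The closing bullet lets the SRC call a DLT, the SAP reports the DLTs that the SRC approved, and PHL cases reach the sponsor as SAEs within a day. This also largely stands. However, the closing bullet covers pre-existing toxicity, and it is arguable whether transaminases raised by metastasis are that. The immune-mediated bullets need a judgement of immune cause and a grade, or a grade and a duration. Neither document says that DLT-like events count in mTPI-2.

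A third reply is that DLTs must be at least Grade 3 as defined in that section, and the documents do not reproduce CTCAE grades. But the 14-day bullet already treats this band as a DLT when bilirubin is normal.

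Two stronger inferences are tempting and unsupported. One is that list ii is out of order throughout, or too loose because 3b exceeds 3 for every b above 1. The first fails against the immediate bullet. The second follows from scaling to baseline, which is a clinical choice. The other is that liver toxicity would go unseen and bias the MTD. SAE reporting and SRC review make an unseen case unlikely.

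**Conclusion.** The point holds as a minor drafting fault in the listed liver criteria. On the stricter reading, every drug-explained rise of >2× to ≤3× baseline with TBL ≥2× ULN is uncovered, including persistent rises that would be DLTs with normal bilirubin. On the looser reading, only those that settle within 14 days are uncovered. The affected group is dose-escalation participants with transaminases raised at baseline by liver metastasis.

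The conclusion assumes that no definition of isolated exists outside the two documents. The frequency of such cases is not given. The target DLT rate is blacked out in the public copies and the decision table is not shown, so the effect of one reclassified event on an escalation decision cannot be calculated.

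**What to change.** State in list ii of Section 10.6.8 that the >2× and >5× baseline bullets apply whether or not bilirubin is raised. This settles the reading and removes the perverse result for persistent rises.

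Optionally, if the safety physicians agree, also set the combined bullet at >2× baseline **and** >3× ULN, with TBL ≥2× ULN and no other explanation. This covers combined rises above both thresholds even if they settle within 14 days. The ULN floor keeps list ii from falling below list i and the PHL range when baseline is under 1.5× ULN. The exact threshold is a clinical decision.

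The cost is a wording change at the next amendment. The downside is that slightly more events may count as DLTs in participants with liver metastasis.

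### Prolonged Grade 3 or higher neutropenia counts as a DLT when uncomplicated but drops out of the definition when an afebrile systemic infection accompanies it

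*Protocol*

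**What the plan says.** Protocol section 10.6.8 opens by tying DLTs to toxicity at or above "Grade 3 toxicity, as defined below, which is not clearly attributable to the disease under investigation", then lists the qualifying events and some exclusions. Neutropenia has two entries, both at Grade 3 or higher:

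- Entry i: "Grade 3 febrile neutropenia regardless of duration ruling out the cause of fever due to non-infections events".
- Entry ii: "Grade 3 neutropenia, without associated fever or systemic infection, which does not improve by at least one grade within 5 days of onset".

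Two neighbouring rules show how the section treats complications elsewhere. For platelets, a DLT at Grade 3 or higher includes "Grade 3 thrombocytopenia, regardless of duration, associated with haemorrhage". Among the exclusions is "Grade 3 or Grade 4 lymphopenia, unless associated with infection".

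An adverse event not on the list "may be defined as a DLT-like event after consultation with the Sponsor and Investigators". SAP section 4.2.1.8 refers to the protocol for the DLT definition, reports the DLTs that the Safety Review Committee (SRC) has approved, and adds no neutropenia criterion.

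**The concern.** Entry ii stops applying once a systemic infection is present, and entry i cannot take over unless there is fever. Afebrile infection during prolonged neutropenia therefore falls between the two. A neutropenic participant with bacteraemia is in a worse position than one with a low count alone, but only the second has a DLT.

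DLT incidence is a primary endpoint. It is also the input to the mTPI-2 rules and, through isotonic regression, to selection of the MTD. The error runs one way: an uncounted DLT either leaves the dose decision unchanged or makes it more permissive. Decisions can be taken on as few as 3 evaluable participants, in a first-in-human trial with no earlier clinical data.

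**Working it through.** **Step 1. Apply the two entries.** Take drug-related, non-immune Grade 3 or higher neutropenia that has not improved by a grade within 5 days, with any complication arising before entry ii has been met.

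| Presentation | Entry i | Entry ii | DLT now | DLT if entry ii applies with or without fever or infection |
|---|---|---|---|---|
| No fever, no infection | no | yes | yes | yes |
| No fever, systemic infection | no (no fever) | no (infection) | **no** | yes |
| Fever from infection | yes | no | yes | yes |
| Non-infectious fever, no infection | no, if the ruling-out phrase is applied | depends on how *associated* is read | unclear | yes |

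The second row fails on every reading. The fourth depends on wording: under a strict reading it is missed (2 of 4 presentations count), and under a softer reading it stays in entry ii (3 of 4 count). The point does not rest on the fourth row.

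Example: non-immune Grade 3 neutropenia from Day 8 to Day 18 is a DLT. Add afebrile bacteraemia on Day 10, before the 5 days are up, and it is not.

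**Step 2. Look for another entry that catches it.**

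- Immune-mediated events: Grade 4 counts outright, and Grade 3 counts if it is one "that does not downgrade to Grade ≤ 2 within 7 days after onset of the event despite maximal supportive care". Both need an immune event, so they narrow the gap without closing it.
- Death: only if the participant dies and the death is not clearly due to disease or extraneous causes.
- Worsened pre-existing toxicity, the entry that holds the SRC-judgement wording: Table 6 requires a neutrophil count of at least 1.5 × 10⁹/L at entry, so Grade 3 or higher neutropenia would normally be new.
- DLT-like events: optional, and the protocol does not say that they enter the mTPI-2 table.

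None closes the gap reliably.

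**Step 3. Size of one missed DLT.** The target rate and equivalence interval are redacted, so I assume targets p_T of 20, 25, 30 and 33% with an interval of ±5 points, a Beta(1,1) prior and intervals 0.10 wide (cut off at 0 and 1). With x DLTs in n, the posterior is Beta(1+x, 1+n−x) with distribution function F. For an interval (a, b),

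UPM = [F(b) − F(a)] / (b − a),

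and the interval with the largest UPM gives the decision, unless P(rate > p_T) reaches 95% with n at least 3. No cell below reaches that limit.

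Worked case, n = 3, target 30%:

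- x = 1: F(p) = 6p² − 8p³ + 3p⁴. Stay interval (0.25, 0.35): (0.4370 − 0.2617)/0.10 = 1.753. Next interval up (0.35, 0.45): (0.6090 − 0.4370)/0.10 = 1.720. Next interval down (0.15, 0.25): 1.522. Decision: stay.
- x = 0: F(p) = 1 − (1 − p)⁴. Stay interval: (0.75⁴ − 0.65⁴)/0.10 = 1.379. Lowest interval (0, 0.05): (1 − 0.95⁴)/0.05 = 3.710. Decision: escalate.

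The same calculation throughout (E escalate, S stay, D de-escalate):

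| True count → count as scored | 20% | 25% | 30% | 33% |
|---|---|---|---|---|
| 1/3 → 0/3 | D → E | D → E | S → E | S → E |
| 1/4 → 0/4 | D → E | S → E | S → E | E → E |
| 1/5 → 0/5 | S → E | S → E | E → E | E → E |
| 2/6 → 1/6 | D → S | D → E | S → E | S → E |

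One missed event changes the decision in 13 of these 16 cells, and always in the permissive direction.

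**The case against.** Five points can be made for the plan.

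1. *The list may not be closed.* The exclusions name events such as fatigue and lymphopenia that have no entry of their own, which would be pointless if only listed events counted. On an open reading, infected neutropenia might already be a DLT, and the lymphopenia comparison carries weight only on that reading. The ambiguity is real. But the lead-in limits DLTs to toxicity as the list defines it, and the separate provision for unlisted events would be unnecessary if they counted by default. The closed reading is the better one.

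2. *The SRC decides.* It reviews all AE, SAE and laboratory data (protocol section 9.6) and approves the DLTs that are reported. This reduces the practical risk. The committee still works from the written definition, which points it to no DLT.

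3. *Infection confounds attribution.* This is a plausible motive for the restriction, but the lead-in already removes events clearly due to a non-drug cause. The restriction is not needed for that purpose.

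4. *The situation is rare.* Agreed. The 3-month GLP study reported no haematology changes, and all the conditions must coincide within 21 days in Part A. Nor does every missed event matter: the table has three unchanged cells, and 1/6 against 0/6 is also escalate either way at 25, 30 and 33%.

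5. *The remedy is incomplete.* Keeping the 5-day condition means that afebrile infection with neutropenia that improves by Day 4 is still not a DLT. That is true. The remedy removes the inversion and does not create a stricter category.

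**Conclusion.** The concern holds. As written, section 10.6.8 does not count prolonged, drug-related, non-immune Grade 3 or higher neutropenia with afebrile systemic infection, although it counts the same neutropenia alone. This rests on the plain wording of the two entries and on reading the list as closed; no redacted figure is needed. Non-infectious fever is a possible second gap that depends on interpretation.

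The frequency cannot be estimated and is probably low. The dose-decision figures are illustrations under assumed targets, an assumed ±5-point interval and a uniform prior. They show that a single event can turn a stay or a de-escalation into an escalation in a small cohort. The definition should be corrected, but the low expected frequency and the SRC's review keep this below the level of a critical fault.

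**What to change.** In section 10.6.8, change entry ii so that it applies *with or without fever or systemic infection*, and keep its grade threshold and its 5-day improvement condition. Leave entry i as it is. Any Grade 3 or higher neutropenia that fails to improve by a grade within 5 days is then a DLT, subject to the attribution clause in the lead-in. Neutropenia that improves within 5 days is classified as before.

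This is one phrase, and it can go into the global amendment that Global Addendum No. 2 already foresees. It needs no added visits or tests. There are two costs. Slightly more events may count as DLTs. And if Part A cohorts have already been evaluated, the sponsor should check whether any earlier event falls in the gap and record how it was classified, so that the DLT counts entering the isotonic regression follow one definition.

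### Section 10.6.8: in an anticoagulated, non-bleeding participant, the DLT list read literally counts 7 days of Grade 1-2 thrombocytopenia but not new-onset, non-immune-mediated Grade 3

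*Protocol*

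**What the plan says.** Section 10.6.8 of the protocol opens by describing a DLT as toxicity of Grade 3 or higher in the 21 days of Cycle 1 of Part A. The event must not be clearly attributable to the disease, other medication "or another non-drug-related aetiology, with modifications or exceptions noted below". A list then follows under "The following toxicities constitute a DLT". Three of its items concern platelets:

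- at or above "Grade 4 thrombocytopenia lasting > 7 days";
- at or above "Grade 3 thrombocytopenia, regardless of duration, associated with haemorrhage";
- under a separate heading for participants on anticoagulation, "Thrombocytopenia below Grade 3 lasting for 7 days, without additional risk factors".

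Three other items can reach thrombocytopenia without naming it. A Grade 4 immune-mediated event is a DLT with no duration condition. A Grade 3 immune-mediated event is a DLT if it has not fallen to Grade 2 or lower "within 7 days after onset of the event despite maximal supportive care including systemic corticosteroids". The last item covers "Any other pre-existing toxicity that has worsened as compared to baseline that is clinically significant and unacceptable" under further conditions, one of which is the SRC's own judgement. An event not on the list "may be defined as a DLT-like event after consultation with the Sponsor and Investigators based on the emerging safety profile". The exclusion list at the end of the section has no thrombocytopenia entry.

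SAP section 4.2.1.8.1 adds no grade criteria. It refers to protocol section 6.6.5, which the current protocol does not contain, and says that reported DLTs are those approved and documented by the SRC.

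**The concern.** A toxicity criterion should not become easier to meet as the event becomes milder. Here the anticoagulation bullet has an upper limit on grade and no lower one, and it stands in the list of events that count. Anticoagulated participants have the most to lose from a low platelet count, yet in them the literal rule can record a DLT for a mild fall and none for a serious one.

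The list defines a primary endpoint, the incidence of DLTs in dose escalation, and it supplies the count that the mTPI-2 table and the MTD estimate use. One DLT more or less in a cohort of three can change the dose decision.

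**Working it through.** **Step 1: apply the list by grade.** Take a participant on anticoagulation with no bleeding and no additional risk factors. The thrombocytopenia is new, falls in the DLT window and is not clearly due to another cause.

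| Platelet event | Not immune-mediated | Immune-mediated |
|---|---|---|
| Grade 1-2 for 7 days | DLT (anticoagulation bullet) | DLT (same bullet) |
| Grade 3, while it stays at Grade 3 | no listed criterion | DLT if not down to Grade 2 or lower within 7 days |
| Grade 4, up to 7 days | no listed criterion | DLT at any duration |
| Grade 4, beyond 7 days | DLT (general criterion) | DLT |

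The middle column is not monotone: it counts the first row, omits the next two and counts the last. With bleeding, Grade 3 or higher is a DLT, so the gap is confined to non-bleeding cases. The item on worsened pre-existing toxicity does not reach a new event.

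**Step 2: can the case arise?** Exclusion criterion 1 (section 5.2) admits participants with recent thromboembolism if adequately treated, and Table 8 does not prohibit anticoagulants. It is probably uncommon. Entry requires platelets of at least 100 x 10^9/L (Table 6), and the 3-month monkey study showed no haematology changes (section 2.3.1). No frequency can be derived.

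**Step 3: what one event does to the dose decision.** The target and equivalence interval are redacted and the decision table is not shown, so the plan's own figures cannot be reproduced. Assumptions: Beta(1,1) prior, targets of 20%, 25%, 30% and 33%, interval of target +/-5 points, other intervals of the same width. With x DLTs in n participants the posterior is Beta(1+x, 1+n-x). The decision is that of the interval with the largest unit probability mass (UPM = interval probability / interval length).

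- 0/3: the posterior is Beta(1,4), whose density falls throughout. The lowest interval therefore has the largest UPM: Escalate at every target.
- 1/3: the posterior is Beta(2,3), with F(p) = 6p^2 - 8p^3 + 3p^4.
 - Target 30%: 0.25-0.35 gives (0.4370 - 0.2617)/0.10 = 1.753. Its neighbours give (0.2617 - 0.1095)/0.10 = 1.522 below and (0.6090 - 0.4370)/0.10 = 1.720 above. Stay.
 - Target 20%: the target interval 0.15-0.25 gives 1.522 and the next one up, 0.25-0.35, gives 1.753. De-escalate.
 - Target 25%: 0.20-0.30 gives (0.3483 - 0.1808)/0.10 = 1.675 and 0.30-0.40 gives (0.5248 - 0.3483)/0.10 = 1.765. De-escalate.
 - Target 33%: 0.28-0.38 gives (0.4900 - 0.3132)/0.10 = 1.768, above both neighbours. Stay.
 - The 95% safety rule is not triggered. The largest P(DLT rate > target) is 1 - F(0.20) = 0.819.

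The same calculation for a lone event in cohorts up to the maximum of 9 (E = Escalate, S = Stay, D = De-escalate):

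| Evaluable | Not counted | Counted, 20% | 25% | 30% | 33% |
|---|---|---|---|---|---|
| 3 | E | D | D | S | S |
| 4 | E | D | S | S | E |
| 5 | E | S | S | E | E |
| 6 or 7 | E | S | E | E | E |
| 8 or 9 | E | E | E | E | E |

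With an interval of +/-3 points, 1/3 still gives Stay or De-escalate at all four targets, while 1/6 and 1/7 at 20% become Escalate. Only the result at 3 participants is stable across these assumptions.

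**The case against.** The strongest reply is that non-bleeding Grade 3 thrombocytopenia is uncounted for every participant, so its absence here is no defect. That is right, and the point does not rest on it. The base rule is at least ordered by severity. The anticoagulation bullet breaks the order by adding Grade 1-2 and nothing above it.

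A second reply is that the bullet may mean a platelet count below the Grade 3 limit, or a deliberately lower threshold that worse events would also meet. Either is possible, and either would remove the inversion. The lead-in does permit departures from Grade 3. But neither meaning is written down, and a reader following the text gets the inverted rule.

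A third is that the lead-in itself makes any Grade 3 toxicity a DLT. It ties that to the definitions that follow, and the provision for unlisted events would be unnecessary if they counted automatically.

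The safeguards are real. The SRC reviews all safety data before a dose decision (section 9.6), reported DLTs are those it approves, and study drug is held or stopped at Grade 3 (section 10.6.6). An unlisted event may be called DLT-like, although neither document says whether that enters the mTPI-2 count. The SRC charter may, but it is not available here. These safeguards limit the consequence. They do not settle the Grade 1-2 event, which the list states is a DLT.

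**Conclusion.** The bullet is wrong as written, and the point is minor. The inversion follows from the text alone. It applies to new-onset thrombocytopenia that is not immune-mediated, in an anticoagulated participant without bleeding or additional risk factors. If such an event were the only candidate DLT among 3 evaluable participants, counting it would change Escalate to Stay or De-escalate for assumed targets of 20% to 33%. Beyond 3 the effect depends on redacted values.

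Three stronger conclusions may be inferred and are not supported. One is that Grade 3 or worse was plainly intended: the documents do not establish the intent. Another is that participants are left unprotected or that the MTD is biased: no frequency is known, the SRC adjudicates, and the dose-hold rule applies regardless of DLT status. The third is that Part A calls have already gone wrong: the SAP amendment history mentions a meeting on Part A outputs, but does not show that any DLT call had been made or was affected.

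**What to change.** Reword the bullet in the next amendment so that it never counts a milder event while omitting a worse one. The sponsor should choose according to intent:

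- Grade 3 or worse thrombocytopenia lasting 7 days or more in a participant on anticoagulation; or
- if a lower threshold is wanted, a stated platelet count or worse for 7 days or more, so that Grades 3 and 4 also qualify; or
- if the bullet was meant as a tolerated exception, delete it. Moving it to the exclusion list would achieve nothing, because the general thrombocytopenia criteria do not reach below Grade 3.

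If the condition about additional risk factors is kept, say which factors and who judges them; the text does not define it. Check any DLT calls already made in Part A for anticoagulated participants with thrombocytopenia.

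The cost is one bullet in an amendment that Global Addendum No. 2 already foresees, with the ethics and regulatory approval that Appendix A 1 requires, plus a short look-back. No extra participants or procedures are needed.
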